3. STUDY PATIENT POPULATION AND DISCONTINUATION

3.1 Inclusion Criteria

Patients must meet the following criteria in order to be included in the research study:

1. Patients with biopsy-proven advanced, unresectable or metastatic, well-to-moderately differentiated (or low-grade) neuroendocrine carcinoma, including typical carcinoid, *CONFIDENTIAL*

STUDY DRUG(S): CARFILZOMIB AMENDMENT 2 DATE: 25 FEBRUARY 2015

pancreatic islet cell and other well- to-moderately differentiated neuroendocrine carcinomas.

- 2. Patients must have at least one unidimensional measurable lesion definable by magnetic resonance imaging (MRI) or computed tomography (CT) scan. Disease must be measurable per Response Evaluation Criteria in Solid Tumors (RECIST) v 1.1 criteria (Appendix E).
- 3. Patients currently receiving or previously treated with single agent somatostatin analogues (e.g. sandostatin LAR[®] or lanreotide) are eligible. However, this is not a mandatory criterion to be included in the study.
- 4. Eastern Cooperative Oncology Group (ECOG) Performance Status score of ECOG PS 0 or 1 (Appendix A).
- 5. Adequate hematologic function defined as:
 - Absolute neutrophil count (ANC) $\geq 1500/\mu L$
 - Hemoglobin (Hgb) $\geq 9 \text{ g/dL}$
 - Platelets $\geq 100,000/\mu L$
- 6. Adequate liver function defined as:
 - Alanine aminotransferase (ALT) ≤ 2.5 x upper limit of normal (ULN) or <5.0 x ULN in patients with liver metastases
 - Aspartate aminotransferase (AST) \leq 2.5 x ULN or \leq 5.0 x ULN in patients with liver metastases
 - Total bilirubin ≤1.5 x ULN (unless the patient has Grade 1 bilirubin elevation due to Gilbert's disease or a similar syndrome involving slow conjugation of bilirubin)
- 7. Adequate renal function defined as serum creatinine ≤2.0mg/dL or calculated creatinine clearance ≥30 mL/min as calculated by Cockcroft and Gault Formula.
- 8. Women of childbearing potential (WoCBP) must have a negative serum or urine pregnancy test. Serum pregnancy test should be performed ≤7 days or urine pregnancy test should be performed within ≤3 days prior to start of treatment. Another pregnancy test will be performed within 30 days following last dose of study drug. WoCBP or men with partners of childbearing potential must use effective birth control measures during treatment (Appendix C). If a woman becomes pregnant or suspects she is pregnant while participating in this study, she must agree to inform her treating physician immediately.
- 9. Predicted life expectancy > 12 weeks
- 10. Age ≥ 18 years.
- 11. All patients must be willing to and have the ability to comply with the study and related follow-up procedures.

CONFIDENTIAL

STUDY DRUG(S): CARFILZOMIB AMENDMENT 2 DATE: 25 FEBRUARY 2015

12. All patients must be able to understand the nature of the study and give written informed consent prior to study entry.

3.2 Exclusion Criteria

Patients who meet any of the following criteria will be excluded from study entry:

- 1. Patients with poorly differentiated neuroendocrine carcinoma, high-grade neuroendocrine carcinoma, adenocarcinoid, globlet cell carcinoid, atypical carcinoid, anaplastic carcinoid, pulmonary neuroendocrine and small cell carcinoma are not eligible.
- Patients who have had radiation therapy, hormonal therapy, biologic therapy, or chemotherapy for cancer within 21 days or 5 half-lives of any chemotherapy or biologic/targeted agent, whichever is longer, prior to first treatment day of the study. (Refer to exclusion criterion #8 for restrictions associated with radiation therapy in patients with brain metastases)
- 3. Patients who have received any other investigational agents within the 21 days or 5 halflives, whichever is longer, prior to first treatment day of the study.
- 4. Women who are pregnant or lactating.
- 5. Patients with poorly controlled or clinically significant atherosclerotic vascular disease including the following:
 - Congestive heart failure (New York Heart Association [NYHA] ≥ Class 3 and 4 heart failure) (Appendix B)
- Patients with known LVEF<40%
- Unstable angina pectoris requiring nitrates within the last 12 months
- Acute myocardial infarction, cerebrovascular accident, or transient ischemic attack within the last 12 months
- Angioplasty (coronary or vascular) within the last 12 months
- Cardiac or vascular stenting in the past 12 months
- Ventricular arrhythmia requiring medication within the last 12 months
- 6. Concurrent severe, intercurrent illness including, but not limited to, ongoing or active infection, or psychiatric illness/social situations that would impair the ability of the patient to receive protocol treatment.
- 7. Major surgical procedures ≤28 days of beginning study drug, or minor surgical procedures ≤7 days. No waiting required following port-a-cath placement.
- 8. Previously untreated brain metastases. Patients who have received radiation or surgery for brain metastases are eligible if therapy was completed at least 2 weeks prior to study entry and there is no evidence of central nervous system disease progression, mild neurologic symptoms, and no requirement for chronic corticosteroid therapy.
- 9. Known diagnosis of human immunodeficiency virus, hepatitis B or hepatitis C.
- 10. Presence of other active cancers or history of treatment for invasive cancer ≤ 5 years. Patients with stage I cancer who have received definitive local treatment at least 3 years previously, and are considered unlikely to recur are eligible. All patients with previously

CONFIDENTIAL

STUDY DRUG(S): CARFILZOMIB AMENDMENT 2 DATE: 25 FEBRUARY 2015 treated in situ carcinoma (i.e., non-invasive) are eligible, as are patients with history of non-melanoma skin cancer.

11. Infection requiring intravenous (IV) antibiotics.

3.3 Discontinuation from Study Treatment

Patients will be discontinued from study treatment for any of the following reasons:

- Disease progression (patients who are receiving clinical benefit in the opinion of the treating investigator may be allowed to stay on study after consultation with the Medical Monitor.)
- Irreversible or intolerable toxicity or abnormal laboratory values thought to be related to drug toxicity
- Conditions requiring therapeutic intervention not permitted by the protocol
- Intercurrent illness (as indicated in the investigator's discretion)
- Inability of the patient to comply with study requirements
- Patient requests to discontinue treatment
- Patient withdraws consent from the study
- Non-compliance/lost to follow-up
- If a patient becomes pregnant during the study period, treatment will be discontinued to avoid harm to fetus.

After discontinuation from protocol treatment, patients must be followed for AEs for 30 calendar days after their last dose of carfilzomib. All new AEs occurring during this period must be reported and followed until resolution, unless, in the opinion of the investigator, these values are not likely to improve, because of the underlying disease. In this case, the investigators must record his or her reasoning for this decision in the patients' medical records and as a comment in the electronic Case Report Form (eCRF).

All patients who have Grade 3 or 4 laboratory abnormalities (per National Cancer Institute Common Terminology Criteria for Adverse Events [NCI CTCAE] v4.03) at the time of discontinuation must be followed until the laboratory values have returned to Grade 1 or 2, unless it is, in the opinion of the investigator, not likely that these values are to improve. In this case, the investigator must record his or her reasoning for making this decision in the patients' medical records and as a comment in the eCRF.

4. **PATIENT REGISTRATION**

The patient must willingly consent after being informed of the procedures to be followed, the experimental nature of the treatment, potential benefits, treatment alternatives, side-effects, risks, and discomforts. Human protection committee (Institutional Review Board [IRB]) approval of this protocol and consent form is required. Eligible patients who wish to participate in the study will be enrolled into the study.

CONFIDENTIAL

STUDY DRUG(S): CARFILZOMIB AMENDMENT 2 DATE: 25 FEBRUARY 2015

Registration must occur prior to the initiation of protocol therapy. Patients eligible to participate in the study may be enrolled through the SCRI Innovations Central Enrollment Desk. The enrollment desk may be reached by calling [name]. Registration may be done via [contact] Monday through Friday, 8:30 a.m. to 4:30 p.m., Central Standard Time, or via email to [contact]. Patient registration will be confirmed via email within 24 hours, or by the next business day.

5. STUDY DESIGN

This Phase II open-label, non-randomized clinical study will be conducted by participating sites in the Sarah Cannon Research Institute network. This study will evaluate the use of carfilzomib for patients with advanced neuroendocrine tumors. For the purpose of this study, patients will receive treatment by IV infusion over 30 minutes on days 1, 2, 8, 9, 15, and 16 of each cycle. Cycles are 28 days in length. Patients will receive 20 mg/m² on Days 1 and 2 of Cycle 1. Thereafter, patients will receive 56 mg/m² on Days 8, 9, 15 and 16. Starting from Cycle 2 patients will receive 56 mg/m² on Days 1, 2, 8, 9, 15 and 16. Patients will be evaluated for response to treatment every 3 cycles; responding and/or stable patients will continue treatment, with re-evaluations every 3 cycles, unless tumor progression or intolerable toxicity occurs. Response to therapy will be assigned using RECIST v1.1criteria (see Appendix E).

The doses to be administered on specific treatment days are outlined in the table below. Patients will receive dexamethasone (4 mg for 20 mg/m² and 8 mg for 56 mg/m²) prior to receiving all carfilzomib doses in Cycle 1 and as needed throughout the study to reduce the severity of infusion reactions associated with carfilzomib. The primary endpoints for this study are ORR and PFS.

The planned enrollment for this study is 62 patients.

The study schema is presented in Figure 1.

CONFIDENTIAL

Day 1 Day 2 Day 8 Day 9 Day 15 Day 16 Day 1 Day 2 Day 8 Day 9 Day 15 Day 16

5.1 Treatment Plan

5.1.1 Carfilzomib

Patients receiving carfilzomib treatment must be hydrated in Cycle 1, and as needed from Cycle 2 onwards, and pre-treated with dexamethasone as indicated below.

Pre-treatment Hydration and Fluid Monitoring

Intravenous (IV) hydration will be given immediately prior to each dose of carfilzomib during Cycle 1; 250 to 500 mL normal saline or other appropriate IV fluid should be given to reduce the risk of renal toxicity and of tumor lysis syndrome (TLS). An additional 250 mL to 500 mL of IV fluids will be given as needed following carfilzomib administration. If lactate dehydrogenase (LDH) or uric acid is elevated (and/or in patients considered still at risk for TLS) at Cycle 2 Day 1, then the recommended IV hydration should be given additionally before each dose in Cycle 2. The goal of the hydration program is to maintain robust urine output (e.g., ≥ 2 L/day). Patients should be monitored periodically during this period for evidence of fluid overload. After Cycle 2, patients will be hydrated at the Investigator's discretion.

If the patient has a dedicated line for carfilzomib administration, the line must be flushed with a minimum of 20 mL of normal saline prior to and after drug administration.

Pre-treatment Dexamethasone

Dexamethasone (4 mg for the 20 mg/m² carfilzomib dose and 8 mg for the 56 mg/m² carfilzomib dose) PO/IV will be administered prior to all carfilzomib doses during the first cycle and as needed in Cycle 2 and beyond. If treatment-related fever, rigors, chills, and/or dyspnea are observed post any dose of carfilzomib after dexamethasone has been discontinued, dexamethasone (8 mg PO/IV) should be re-started and administered prior to subsequent doses.

TREATMENT SCHEDULE

Carfilzomib 20 mg/m² IV will be administered over 30 minutes (\pm 5 minutes) on Days 1 and 2 of Cycle 1, followed by escalation to 56 mg/m² IV over 30 minutes (\pm 5 minutes) on Days 8, 9, 15, and 16 of Cycle 1. For patients who have adequately tolerated dosing during Cycle 1, carfilzomib 56 mg/m² IV will be administered over 30 minutes (\pm 5 minutes) on Days 1, 2, 8, 9, 15, and 16 of Cycle 2 and beyond. Patients may continue study treatment until intolerable

CONFIDENTIAL

STUDY DRUG(S): CARFILZOMIB AMENDMENT 2 DATE: 25 FEBRUARY 2015

toxicity, confirmed progressive disease (PD), withdrawal of consent, death, or study closure, whichever occurs earliest. The treatment schedule is provided in the table below.

DRUG	DOSE	CYCLE	FREQUENCY	Route of Administration
Carfilzomib ^{a, c}	20 mg/m ²	Cycle 1 only	Days 1, 2	IV over 30 minutes
Carfilzomib ^a	filzomib ^a 56 mg/m ² Cycle 1 only Days 8, 9, 15		Days 8, 9, 15, 16	IV over 30 minutes
Carfilzomib ^{b, c}	56 mg/m^2	Cycle 2 and beyond	Days 1, 2, 8, 9, 15, 16	IV over 30 minutes

Table 1Overall Treatment Plan

^a Carfilzomib 20 mg/m² IV will be infused over 30 minutes (\pm 5 minutes) on Days 1 and 2 of Cycle 1, followed by escalation to 56 mg/m² infused over 30 minutes (\pm 5 minutes) on Days 8, 9, 15, and 16 of Cycle 1.

^b Carfilzomib 56 mg/m² IV will be infused over 30 minutes (\pm 5 minutes) on Days 1, 2, 8, 9, 15, and 16 of Cycle 2 and beyond.

 $^{\rm c}$ Study drug will be taken within $\pm\,2$ days of the scheduled study day for Day 1 of each Cycle.

Carfilzomib will be administered within ± 2 days of the scheduled study day for Day 1 of each Cycle. Every effort should be made to maintain the dosing schedule as outlined above, and if this is not possible due to extenuating circumstances then priority should be given to maintain consecutive dosing days. If a mid-cycle dose is missed, that dose should be administered no more than 2 days after the scheduled dosing day. Anticipated treatment changes outside of the 2-day window must be discussed with the Medical Monitor or designee.

5.2 Treatment Duration

Patients will be evaluated for toxicity at the start of each cycle. Every 3 cycles, restaging will occur with imaging, laboratory chemistries, and tumor markers as defined in Appendix D. Patients will continue on treatment until progression as defined in Appendix E or intolerance to side effects.

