5.4 Correlative Studies

5.4.1 Tumor Tissue Samples

Archival tumor samples may be collected during the study with the purpose of identifying molecular alterations relevant to carfilzomib.

6. **DOSE MODIFICATIONS**

If toxicity occurs, the toxicity will be graded utilizing the NCI CTCAE v4.03 (https://evs.nci.nih.gov/ftp1/CTCAE/CTCAE), and appropriate supportive care treatment will be administered to decrease the signs and symptoms thereof. Dose adjustments will be based on the organ system exhibiting the greatest degree of toxicity.

CONFIDENTIAL

STUDY DRUG(S): CARFILZOMIB AMENDMENT 2 DATE: 25 FEBRUARY 2015

Doses of carfilzomib will be modified based on hematologic and non-hematologic toxicity. If dose reductions are necessary, they will be permanent for the remainder of the treatment. Carfilzomib may be adjusted according to the dose modification tables that follow. If the patient is receiving the lowest allowable dose and experiences a toxicity requiring a dose reduction, the offending study drug should be discontinued. Any patient requiring a toxicity-related dose delay of more than 21 days from the intended day of the next scheduled dose must be discontinued from the study.

If patients experience any dose-related toxicity at 20 mg/m^2 , they must be discontinued from the study.

A maximum of two dose reductions are allowed in this study. If more than two dose reductions are necessary for a patient, the patient will be discontinued from study treatment.

The dose level reductions to be used in this study are presented in Table 2.

Dose Level	Carfilzomib
Starting Dose	56 mg/m^2
Dose Level -1	45 mg/m ²
Dose Level -2	36 mg/m ²

Table 2Dose Level Modifications

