c Patients who require a treatment delay of more than 3 weeks due to treatment-related toxicity will be discontinued from study treatment, unless the treating physician and the Study Chair agree that continued treatment at lower doses is in the best interest of the patient.

CONFIDENTIAL

STUDY DRUG(S): CARFILZOMIB AMENDMENT 2 DATE: 25 FEBRUARY 2015

Table 3Carfilzomib Dose Modifications for Hematologic Toxicities (continued)

AE Term and Description	Dose Modification
FEBRILE NEUTROPENIA	
Grade 3 ANC <1.0 x $10^9/L$, fever $\ge 38.5^{\circ}C$	 Interrupt study treatment until ANC recovery to ≤ Grade 2^a (ANC ≥ 1.0 x 10⁹/L) and resolution of fever <38.5°C. Restart treatment with a 1 level dose- reduction.
Grade 4 ANC <1.0 x 10^{9} /L, fever \geq 38.5°C and life- threatening consequences	 Interrupt study treatment until ANC recovery to ≤ Grade 2^a (ANC ≥ 1.0 x 10⁹/L) and resolution of fever <38.5°C and any complications. Restart treatment with a 1 level dose- reduction

a Hold carfilzomib treatment; do at least weekly CBC with differential until toxicity resolves (ANC recovery $\geq 1.0 \times 10^{9}$ /L and platelets $\geq 75 \times 10^{9}$ /L).

b Re-treatment criteria = ANC recovery $\geq 1.0 \text{ x } 10^{9}/\text{L}$ and platelets $\geq 75 \text{ x } 10^{9}/\text{L}$.

c Patients who require a treatment delay of more than 3 weeks due to treatment-related toxicity will be discontinued from study treatment, unless the treating physician and the Study Chair agree that continued treatment at lower doses is in the best interest of the patient.

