7.4 Response Assessment Every 3 Cycles

Patients will be evaluated for response to treatment after every 3 cycles of treatment. The following assessments will be performed:

- CT scans of chest, abdomen and pelvis (if abnormal at baseline)
- 24 hour urine for 5-HIAA

Patients with progressive disease or unacceptable toxicity should be discontinued from the study; patients with stable disease or response to therapy will continue treatment.

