7.6 Follow-up

7.6.1 Follow-up for Patients Who Discontinue Prior to Disease Progression

Patients who discontinue study treatment prior to the occurrence of disease progression will be followed every 3 months (± 1 month) from the date of last dose of study drug until disease progression. Tests to be performed are listed in Appendix D. Patients will not be followed up for survival if they start any subsequent therapy.

The following tests will be done during follow up visits:

- Medical history will be updated
- Physical examination, including weight and vital signs (includes blood pressure, heart rate, breathing rate, and oral temperature)
- CBC, including 3-part differential and platelets
- CMP
- 24-hour urine collection for 5-HIAA testing
- CT scan of the chest, a CT scan of the abdomen/pelvis .

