Appendix D: Schedule of Assessments (continued)

- a Baseline procedures including medical history, physical examination, peripheral neuropathy assessment, 12-lead ECG, ECOG PS, CBC, CMP, PT/PTT/INR, and serum or urine pregnancy test should be done \leq 7 days prior to initiation of treatment. However, if these initial examinations are obtained within 72 hours of Cycle 1 Day 1 they do not have to be repeated. Scans should be performed \leq 28 days prior to initiation of treatment, to document measurable or evaluable disease.
- b Physical examination will include measurements of height (pre-treatment visit only), weight, and vital signs.
- c Vital signs will include resting heart rate, blood pressure, respiratory rate, and temperature.
- d ECHO with calculated LVEF (repeat if/when clinically indicated). MUGA is acceptable if ECHO is not available.
- e CMP will include measurements of glucose, BUN, creatinine, sodium, potassium, chloride, calcium, CO², ALP, AST, ALT, total bilirubin, total protein, and albumin.
- f If PT/PTT/INR are normal at baseline they do not need to be repeated. Patients requiring the initiation of an anti-coagulation therapy during study treatment should have coagulation tests performed according to standard practice guidelines.
- g Serum or urine pregnancy tests are to be conducted in women of childbearing potential at the beginning of the study and at the end of study visit or 30 days post last dose..
- h If available, archival tissue samples will be requested by study site personnel.
- i Fasting (overnight) serum chromagranin A test will be done during screening and then on Day 1 of each cycle.
- j 24 hour urine for 5-HIAA will be done during screening and then every 3 cycles to assess response.
- k CT scans of the chest \leq 4 weeks prior to initiation of treatment and then every 3 cycles during the treatment and at the end of study visit, if no PD and not done within prior 6 weeks.
- 1 CT scans of the abdomen/pelvis \leq 4 weeks prior to initiation of treatment and then every 3 cycles during the treatment and at the end of study visit.
- m Patients should visit the study center \leq 30 days for end-of-treatment assessments. Patients must be followed for AEs for 30 calendar days after the last dose of study drug.

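### On-treatment tumour scans are counted in cycles with no calendar anchor, so a dosing delay that moves Day 1 also moves the next scan and, on average, postpones recorded progression

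*Combined protocol and SAP*

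**What the plan says.** Section 5.2: "Every 3 cycles, restaging will occur with imaging, laboratory chemistries, and tumor markers as defined in Appendix D". Section 7.4: "Patients will be evaluated for response to treatment after every 3 cycles of treatment". Appendix D footnote k schedules chest CT at baseline "and then every 3 cycles during the treatment and at the end of study visit, if no PD and not done within prior 6 weeks", and footnote l uses the same three-cycle interval for abdomen and pelvis. Sections 5 and 10.5.2 also count in cycles. The only link to the calendar is the nominal cycle length in Section 5: "Cycles are 28 days in length".

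Treatment holds for toxicity are part of the regimen (Tables 3 to 5). Section 6 limits a single delay: "Any patient requiring a toxicity-related dose delay of more than 21 days from the intended day of the next scheduled dose must be discontinued". Table 3 footnote c sets a similar three-week limit but allows an exception, "unless the treating physician and the Study Chair agree that continued treatment at lower doses is in the best interest of the patient". The two passages should be reconciled.

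Patients who stop treatment before progression leave the cycle clock. Section 7.5 and Appendix D provide CT at the end of treatment, and under Section 7.6.1 these patients "will be followed every 3 months (± 1 month) from the date of last dose of study drug".

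Section 10.4.1 measures PFS from first dose to RECIST progression or death on study, and censors at the last tumour assessment. It has no rule or sensitivity analysis for late scans.

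**The concern.** Radiological progression can be recorded only when a scan is done. If the scan date follows dosing, then among patients still on treatment, those with delays are scanned at longer intervals than those without. Their progression is recorded later on average, with no change in the disease. First response, its confirmation and the stage 1 read-out can slip in the same way.

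The trial has one arm, so PFS can be read only in absolute terms or against outside figures such as those in Sections 1.2 and 1.3. A shift created by the scan calendar enters that reading directly. The weight of the point also depends on the status of PFS, which the protocol leaves unclear: it is secondary in Section 2.2 but called primary in Section 5.

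**Working it through.** **The plan's own design figure.** Section 10.2 is the only computed design. Stage 1 stops at 0 or 1 response in 23, and the null is rejected at 6 or more responses in 56. Summing P(X1 = x)·P(X2 ≥ 6 − x) over x = 2 to 23, with 33 patients in stage 2, gives a type I error of 0.04996 at a response rate of 0.05 and power of 0.8003 at 0.15. Both match the stated 0.05 and 80%. The scan interval does not enter this calculation. PFS has no target, power or sample size to reproduce.

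**Inputs for the PFS check.**
- On-time interval: 3 × 28 = 84 days (Section 5).
- Largest single toxicity delay under Section 6: 21 days. One such delay puts the first scan at 84 + 21 = day 105. A 21-day delay in each of three cycles puts it at 84 + 63 = day 147.
- True median PFS (assumption): 5.5 to 16.4 months, taken from PFS figures the protocol cites for other trials. It states none for carfilzomib.
- Progression times exponential; one month = 30.4375 days; deaths ignored (they are dated exactly and do not shift).
- Delay frequency: not given, so it is varied.

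**Mean lag from progression to the next scan.** For scan interval D and rate λ = ln 2 / median, the mean lag is D / (1 − exp(−λD)) − 1/λ.

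Example at 5.5 months (167.4 days): λ = 0.00414 and 1/λ = 241.5. For D = 84, 84/0.2938 − 241.5 = 44.4 days. For D = 105, 105/0.3526 − 241.5 = 56.3 days. The shift is 11.9 days.

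| Days lost in every 3-cycle block | Interval (days) | Mean lag (days), true median 16.4 to 5.5 months | Shift against 84 days |
|---|---|---|---|
| 0 | 84 | 42.8 to 44.4 | 0 |
| 7 | 91 | 46.5 to 48.4 | 3.6 to 3.9 |
| 21 | 105 | 53.8 to 56.3 | 11.0 to 11.9 |
| 42 | 126 | 64.8 to 68.5 | 22.0 to 24.0 |
| 63 | 147 | 76.0 to 80.9 | 33.2 to 36.5 |

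A simulation of 400,000 progression times gives the same shifts to within about 0.1 day.

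**One 21-day delay in the first three cycles only.** Scans fall at day 105 and every 84 days after that. The mean recorded time is 105 + exp(−105λ)·84/(1 − exp(−84λ)), against 84/(1 − exp(−84λ)) on time. The difference is 4.18 days at a median of 5.5 months and 1.49 days at 16.4 months if every patient is delayed. If 30% are delayed, multiplying by 0.30 gives 1.25 and 0.45 days. The average is small because the shifted grid finds some progressions sooner: one at day 95 is found at day 105 instead of day 168. For a patient who has progressed by day 84 (29% at 5.5 months, 11% at 16.4 months), the recorded date moves by the full 21 days.

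**Recorded median.** With scans on a grid, the recorded median is the first scan on or after the true median.

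| True median (months) | 84 days | 105 days | 147 days |
|---|---|---|---|
| 5.5 | 5.52 | 6.90 | 9.66 |
| 9 | 11.04 | 10.35 | 9.66 |
| 11 | 11.04 | 13.80 | 14.49 |

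At 9 months the recorded median falls as the interval lengthens. The median is therefore not a reliable measure of this effect; the mean lag is.

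**The case against.** The strongest case against is that the effect is small, that the protocol partly contains it, and that no decision depends on it. Much of this stands.

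- **The median.** A reader who takes a true median of 5.5 months might infer that delays inflate median PFS to 6.9 or 9.7 months. That is a grid artefact: 167.4 days lies just under the on-time scan at day 168, so the on-time case shows almost no bias. Other plausible medians give no change or a decrease.
- **The 147-day interval.** This needs 21 days lost in every cycle. Most long holds in Tables 3 and 4 force a dose reduction, and Section 6 allows at most two. Some holds carry no reduction, so repeated delays are possible, but the documents do not support 147 days as an interval for the whole cohort.
- **Which holds count.** A reader might assume that every hold moves the next scan. Section 5.1.1 allows a missed mid-cycle dose to be given only up to 2 days late, so some holds may be skipped doses that leave Day 1 where it was. The text does not settle this.
- **Who is affected.** A reader might infer that the patients with the worst toxicity are scanned least often. Many of them stop treatment and then come under the end-of-treatment CT and calendar follow-up.
- **Consequence.** PFS is a descriptive single-arm estimate with no hypothesis or decision rule.

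None of this supplies the missing calendar anchor. Where Day 1 moves, so does the scan, and no section limits the accumulated drift or handles it in the analysis.

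**Conclusion.** The concern holds as a modest scheduling weakness that is cheap to correct. In patients who stay on treatment with delays that move Day 1, recorded progression is later on average. The mean shift runs from about 0.4 to 4 days for a single early 21-day delay, through about 4 days and 11 to 12 days when 7 or 21 days are lost in every three-cycle block, to 33 to 37 days in the extreme case. These figures rest on exponential progression, an assumed true median of 5.5 to 16.4 months, and delay patterns chosen for illustration.

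The documents do not support a claim that the reported median PFS will be inflated by a given amount, or that it will be inflated at all. The Simon type I error and power are unaffected; only the timing of response and stage 1 assessments can slip.

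**What to change.** In Sections 5, 5.2, 7.4 and 7.6.1 and in Appendix D, schedule tumour assessments every 12 weeks (±7 days) counted from Cycle 1 Day 1, regardless of dose delays or treatment discontinuation, until progression. This removes the delay-driven shift apart from the window. The ordinary lag of a 12-week grid, about 43 to 44 days on average, remains.

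Restate the stable-disease part of the Clinical Benefit Rate in Section 10.4.1 to match. It now requires at least 6 cycles, nominally 6 × 28 = 168 days. Use at least 24 weeks and allow for the scan window, since a week-24 scan may fall as early as day 161. Otherwise a delayed patient's week-24 scan would come before six cycles are complete.

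The cost is amendment wording. Scan frequency on treatment is unchanged when nothing is delayed. Some scans will fall off the cycle boundary, and patients with holds may be scanned earlier than now. Off treatment, 12 weeks ±7 days is slightly more frequent and tighter than 3 months ±1 month. No dosing rule changes.
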